7.1 Descriptive Analyses

Descriptive statistics will be presented for baseline characteristics described in Section 4.5. Statistical testing for differences in baseline characteristics between groups will not be conducted as differences in these characteristics are due to chance.^{29, 31} Descriptive statistics will be presented by intervention group using means and standard deviations for continuous variables, and frequencies and percentages for categorical variables. See Appendix A for a table containing all study outcomes and variables.

7.2 Covariate Adjustments, Subgroup Analyses, and Sensitivity Analyses

Models will be adjusted for baseline values of each outcome, blocking variables, and covariates specific to each outcome, which are described in the manuscript sections.

Subgroup analyses will be conducted for one outcome in each paper. These analyses are described in each manuscript section.

We will conduct per protocol sensitivity analyses for each outcome wherein data for participants who did not adhere to their assigned group will be removed from the analysis. We will also conduct as-treated sensitivity analyses for each outcome wherein participants will be analyzed based on their incentive usage by 1) using pre-specified cut points based on percentage of incentives redeemed (25%, 50%, 75%), 2) basing usage on weeks used wherein participants who earned the incentive ≥ 27 weeks will be analyzed as part of the FoodRx group and participants who earned the incentive ≤ 26 weeks will be analyzed as part of the comparison group, and 3) basing usage on incentive level by comparing single households to the remaining levels (i.e., 2+ households and above). Additional sensitivity analyses are described in each manuscript section.

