The second element was a weekly healthy food incentive of CDN\$10.50 per household member for 12 months. Participants earned the weekly incentive by purchasing whole, minimally processed foods with little to no added fat, sugar, or salt from all food groups in study-affiliated supermarkets, which were part of a large chain with multiple banners and locations.^{8, 39} Incentive-eligible foods included dairy products; whole grain bread, pasta, and cereal; fresh, frozen, and canned vegetables; fresh and frozen fruit; fresh, plain meats, fish, and poultry; canned fish and meat alternatives (eggs, canned and dried beans, plain almonds). Researchers calculated incentive amounts based on total household size as reported at baseline (0 months), which was communicated to participants after randomization. Once participants reached their spending threshold as defined by their household size, they immediately received loyalty card points equal to their eligible spending (e.g., a two-person household spending CDN\$21 received CDN\$21 in points). The incentive was capped at CDN\$10.50 per person per week, and points were only given to households that met or exceeded their threshold each week. Although progress towards meeting the minimum spend was reset weekly, earned points carried over between weeks, did not expire, and could be redeemed for anything in-store in CDN\$10 increments. However, participants were encouraged to use these points to continue the earn-reward cycle by purchasing incentive-eligible foods. At baseline, participants' loyalty cards were preloaded with points equivalent to one week's incentive amount to allow initial participation without paying out-of-pocket. The incentive redemption mechanism was pilot tested⁴⁰ and is fully described elsewhere.³²

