3.4 Randomization and Blinding

Prior to randomization, participants completed baseline data collection and received the healthy food prescription. Researchers randomized participants to either the FoodRx (n=299) or comparison (n=297) group with a 1:1 allocation ratio using a computer-generated, concealed, blocked randomization sequence in REDCap (Research Electronic Data Capture)⁴¹ created by an independent statistician. Blocking variables included gender identity (woman, man), recruitment location (urban setting, rural setting, Indigenous primary care clinic), and baseline A1C (6.5-8.5%, 8.6-12%). The intervention group received both a healthy food prescription and a healthy food incentive. The comparison group received a healthy food prescription alone.

Due to the nature of the intervention, participants were not blinded to their allocation; however, they were blinded to study objectives. Participants in the comparison group were also blinded to the details of the healthy food incentive, including its monetary value and eligible foods. Care providers and researchers who collected and analyzed the data were blinded to treatment allocation with the exception of a research assistant who assisted participants in the intervention group throughout the trial.

4. Trial Population

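### As-treated rule 2 counts FoodRx participants who earned the incentive in up to 26 weeks as comparison participants, so its contrast is neither randomised nor clean

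*SAP*

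**What the plan says.** SAP section 7.2 plans per-protocol and as-treated sensitivity analyses for each outcome.

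- **Per-protocol:** "data for participants who did not adhere to their assigned group will be removed from the analysis". Adherence is not defined for either arm.
- **As-treated rule 1:** cut points at 25, 50 and 75 percent of incentives redeemed. Where people below a cut point go is not stated.
- **As-treated rule 2:** those who earned the incentive in 27 or more weeks are analysed as FoodRx, while "participants who earned the incentive ≤ 26 weeks will be analyzed as part of the comparison group".
- **As-treated rule 3:** "basing usage on incentive level by comparing single households to the remaining levels". No move between arms is described.

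On exposure, section 3.4 says "The comparison group received a healthy food prescription alone". Section 3.2 says "points were only given to households that met or exceeded their threshold each week", and that at baseline "participants' loyalty cards were preloaded with points equivalent to one week's incentive amount". Section 5.4.1 sets the maximum at 52 weeks. Section 7.4 lists as-treated analyses for 12-month A1C and also for 6-month A1C. Section 6.3 makes intention-to-treat the analysis for all outcomes, and section 6.5 calls the sensitivity analyses exploratory.

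**The concern.** A comparison participant has zero incentive weeks by design, so rule 2 can only move people out of FoodRx and into the comparison group. This has three consequences.

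1. **The comparator is contaminated.** It mixes people who received no incentive with people who may have earned it in up to 26 of 52 weeks.
2. **The groups are formed after randomisation.** Reaching 27 weeks requires meeting a weekly spending threshold and staying in the program at least that long. No comparison participant faces either condition. FoodRx participants who leave in the first half fall into the comparison group whenever their A1C is known, and section 5.1 allows it to come from medical records.
3. **At 6 months the rule looks past the outcome.** Half of 52 weeks is 26, so nobody can have earned 27 weeks by the 6-month visit. Either everyone is classed as comparison, or the group is set by behaviour after the outcome was measured. The dose-response analysis in section 7.4 limits redemption to the first 6 months for the mid-intervention analysis; rule 2 has no such window.

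At stake is the reading of an analysis repeated across six manuscripts. A larger as-treated than intention-to-treat difference could be taken as evidence that the incentive works when used, and rule 2 cannot support that.

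**Working it through.** **The plan's own figure.** The SAP gives no figure for these analyses. The only scale comes from section 4.2: SD 1.4% and a clinically meaningful difference of 0.5%. Those inputs do reproduce the sample size: 165 per arm at 90% power and two-sided 5% (sidedness assumed), then 330 × 1.25 / 0.70 = 589, or 592 with rounding up per arm, against 594 stated. Nothing below depends on 594.

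**Inputs.** Arm sizes are 299 and 297 (section 3.4). Two quantities are assumptions, because the SAP gives neither: p, the share of FoodRx earning 26 or fewer weeks, and g, the A1C gap (low minus high users) that has nothing to do with the incentive.

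**Spurious benefit with no true effect (unadjusted).** Set the comparison-arm mean to 0.

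- High users: -p·g. Low users: +(1-p)·g.
- Rule 2 comparator mean: 299p(1-p)g / (297 + 299p).
- Rule 2 contrast: -p·g - 299p(1-p)g / (297 + 299p).

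With p = 0.5 and g = 0.42 (0.3 × 1.4): -0.21 - (149.5 × 0.21)/(297 + 149.5) = -0.21 - 31.4/446.5 = **-0.28%**, or 56% of 0.5%.

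Other inputs, with false-positive rates from 3,000 simulated trials each (unadjusted, SD 1.4%, two-sided 5%):

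| p | g | Rule 2 contrast | False-positive rate |
|---|---|---|---|
| 0.2 | 0.3 | -0.10 | 14% |
| 0.3 | 0.5 | -0.23 | 49% |
| 0.5 | 0.7 | -0.47 | 95% |
| 0.2 to 0.5 | 0 | 0.00 | about 5% |

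Keeping the randomised arms gave a mean difference of 0.00 and 4% to 6% rejection in every scenario.

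**Dilution with a true effect.** Suppose every FoodRx participant gains 0.5% and g = 0. Moved recipients form 299p/(297 + 299p) of the comparator: 17% at p = 0.2 and 33% at p = 0.5. The contrast shrinks to -0.5 × (1 - 0.168) = -0.42% and -0.5 × (1 - 0.335) = -0.33%.

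**Both together.** At p = 0.5 the spurious part is 0.667·g (0.28/0.42) and the dilution is 0.5 - 0.333 = 0.167. They cancel at g = 0.167/0.667 = 0.25%. A larger gap overstates the true effect, and a smaller or reversed gap understates it.

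**Effect of baseline adjustment.** If the 0.42% gap is already present at baseline and the baseline-to-12-month correlation is 0.5 to 0.7 (assumed, equal SDs), the unexplained gap is 0.42 × (1 - r) = 0.21 to 0.13. The contrast of -0.28% falls to -0.28 × (1 - r) = -0.14% to -0.08%.

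**Alternative exposures.** With randomised arm as instrument, the simplest estimate is the intention-to-treat difference divided by mean weeks earned in FoodRx. With no true effect the expected numerator is 0 for any p and g. A binary exposure of 27 or more weeks would not do: if everyone gains 0.5% and half reach 27 weeks, it gives -0.5/0.5 = -1.0%, double the truth.

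**The case against.** The strongest reply is that little rests on these analyses. Section 6.3 makes intention-to-treat the analysis, section 7.4 defines the primary test that way, and section 6.5 rests inference on the single primary outcome and calls the sensitivity analyses exploratory. This stands, and it limits the weight of the point. It does not make a mixed comparator informative, and nothing in section 7.2 warns that rule 2 is outside the protection of randomisation.

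Second, the illustrated sizes are unadjusted. The planned model adjusts for baseline A1C and several covariates, and a stable level gap would cancel in a pure change contrast. This stands for the size: only the gap that the covariates leave unexplained matters. It does not remove the problem. The 12-month A1C covariates omit food-insecurity severity, household income and insulin use, which plausibly bear on both threshold spending and A1C. Income and insulin use are listed only as possible auxiliary variables for missing data, and severity and insulin use as subgroup factors. No weighting or instrumental-variable method is given for this analysis.

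Two stronger readings are tempting and are not supported. A reader might infer that all the as-treated analyses move low users into the comparison arm. Only rule 2 says so: rule 1 is silent and rule 3 contrasts household sizes. A reader might also infer that the per-protocol analysis drops low users from FoodRx. The sentence is worded for both arms and sets no usage threshold. One-sided removal is likely, because the prescription was given once, before randomisation, and the comparison arm has no evident way to be non-adherent. But that is an inference; what the text shows is that adherence is undefined.

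**Conclusion.** The concern holds for as-treated rule 2. It moves participants in one direction only, on post-randomisation behaviour, and places partly treated people in the comparator. For 6-month A1C its 27-week cut cannot be met before the outcome. The per-protocol rule probably shares the one-sided problem, but this cannot be settled while adherence is undefined.

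The size is not knowable from the SAP. The figure of about -0.28% rests on no true effect, half of FoodRx below 27 weeks, a 0.42% gap and no adjustment; with the baseline-adjustment assumptions above it would be -0.08% to -0.14%. These are illustrations, not predictions. The direction of the gap is itself assumed, and dilution works against it, so it would be wrong to infer that rule 2 must favour FoodRx. Nor does the point cast doubt on the primary intention-to-treat result. It should be corrected before the as-treated results are reported.

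**What to change.** 1. **Continuous outcomes, including 12-month A1C.** Replace rule 2 with an instrumental-variable (complier-type) analysis that keeps everyone in the randomised arm. Use randomised group as the instrument and weeks earned up to the outcome visit (0 in the comparison arm) as a continuous exposure, with the same baseline covariates. State the assumptions: the effect is linear in weeks, and assignment acts only through weeks earned. Say that preloaded points and unblinded assignment strain the second.
2. **Do not use 27 or more weeks as a binary instrumented exposure.** Participants with 1 to 26 weeks are partly treated, so the estimate is inflated.
3. **Non-continuous outcomes, or wherever rule 2 or the per-protocol rule is kept.** Label the result a non-randomised descriptive comparison, count only weeks before the outcome visit, and draw no effectiveness statement from it.
4. **Definitions.** Define adherence for each arm in the per-protocol rule, and state under rule 1 where participants below each cut point are placed.

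The cost is SAP wording and a standard two-stage model in Stata or R on data already planned for. The price is wider intervals. Linear two-stage methods do not carry over directly to the logistic, ordinal, Tweedie and Poisson models, which is why those outcomes get the descriptive label.

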7.3 Role of Wahkohmakanah, Niiksokowaaks, All My Relations

This section describes the role of Wahkohmakanah (Cree), Niiksokowaaks (Blackfoot), All My Relations (English), the FoodRx Indigenous Advisory Board, herein referred to as AMR.

Subgroup analyses of Indigenous participants may be included in each manuscript, as determined by AMR members. AMR is embedded in the FoodRx research team and will be available to contextualize each analysis. In accordance with Indigenous Data Governance, specifically OCAP® principles¹²¹, AMR and the FoodRx principal investigators will retain co-ownership and governance of the data and results specific to Indigenous participants in FoodRx. AMR will decide which results to report and how they will be presented in each manuscript. Once all

analyses are complete, AMR may choose to develop a summary discussion paper synthesizing all results for Indigenous participants.

7.4 Primary Manuscript

This paper will report results for 12-month A1C, our primary outcome, along with secondary and exploratory outcomes at 6-, 12-, and/or 18-months, including blood glucose levels, clinical health markers, and need for antihyperglycemic medication.

12-month A1C, Primary Outcome

We will assess the intention to treat effect of group assignment on mean A1C at 12-months as a continuous outcome using mixed-effects linear regression. The primary test will be the group \times time interaction contrast at 12-months (i.e., post-intervention), which estimates between-group differences in mean A1C from baseline to 12 months. Models will be adjusted for baseline A1C to estimate treatment effect while holding baseline A1C constant, and additional blocking variables (gender, recruitment location). To improve the precision of effect estimates, models will also be adjusted for age, race/ethnicity, educational attainment, number of children living in the home, and diabetes duration. Additionally, all models will include a data source indicator variable (study measured vs administrative health data), group (FoodRx vs comparison), collection timing (number of days measurement was taken since baseline), and restart cohort indicator variable (did not restart vs did restart). We will include random intercepts for participants (participant study ID) to account for within-subject correlation due to repeated measures, and for primary care clinics (clinic study ID) to account for clustering of participants within clinics. Missing data for covariates will be addressed using full information maximum likelihood.

We will conduct subgroup analyses for 12-month A1C by baseline household food insecurity severity (marginal, moderate, severe), gender (man, woman, gender diverse), recruitment location (urban setting, rural setting, Indigenous primary care clinic), Indigenous identity, baseline A1C ($\leq 8.5\%$, $\geq 8.6\%$), and baseline insulin use (no, yes).

We will conduct dose-response analyses to examine whether 12-month A1C differs based on the total value of incentives redeemed, a continuous variable, in the first 6 months for the mid-intervention analysis, and in the full 12-months for the post-intervention analysis.

In addition to per-protocol and as-treated analyses, we will conduct sensitivity analyses for 12-month A1C to examine 1) the impact of excluding A1C values obtained from administrative health data, 2) if findings differ when models include all participants regardless of A1C source, and a collection timing indicator variable (time since baseline, deviation from 12-month data collection timepoint), 3) the impact of using multiple imputation for missing data rather than full information maximum likelihood, 4) the impact of adjusting for changes in medication/insulin type and dosage between baseline and post-intervention follow-up, 5) the impact of including the first measure of baseline A1C collected before the trial was restarted, and 6) the impact of excluding participants who restarted the trial.

Blood Glucose Levels, Secondary Outcomes

6-month A1C We will assess group differences in 6-month A1C (i.e., mid-intervention) as a continuous outcome using mixed-effects linear regression. Models will be adjusted for baseline A1C, and additional blocking variables (gender, recruitment location). To improve the precision of effect estimates, models will also be adjusted for age, race/ethnicity, educational attainment, number of children living in the home, and diabetes duration. Models will also include group (FoodRx vs comparison), and baseline A1C data source (study measured vs administrative health data) indicator variables. We will include random intercepts for participants (participant study ID) to account for within-subject correlation due to repeated measures, and for primary care clinics (clinic study ID) to account for clustering of participants within clinics.

In addition to per-protocol and as-treated analyses, we will conduct sensitivity analyses for 6-month A1C to examine 1) the impact of excluding A1C values obtained from administrative health data, 2) if findings differ when models include all participants regardless of A1C source, and a collection timing indicator variable (time since baseline, deviation from 6-month data collection timepoint), 3) the impact of using multiple imputation for missing data rather than full information maximum likelihood, 4) the impact of adjusting for changes in medication/insulin type between baseline and mid-intervention follow-up, and 5) the impact of including the first measure of baseline A1C collected before the trial restart.

18-month A1C We will assess group differences in 18-month A1C (i.e., 6-months post-intervention) as a continuous outcome using mixed-effects linear regression. Models will be adjusted for baseline A1C, and additional blocking variables (gender, recruitment location). To improve the precision of effect estimates, models will also be adjusted for age, race/ethnicity, educational attainment, number of children living in the home, and diabetes duration. Models will also include group (FoodRx vs comparison), and baseline A1C data source (study measured vs administrative health data) indicator variables. We will include random intercepts for participants (participant study ID) to account for within-subject correlation due to repeated measures, and for primary care clinics (clinic study ID) to account for clustering of participants within clinics.

In addition to per-protocol and as-treated analyses, we will conduct sensitivity analyses for 18-month A1C to examine 1) the impact of excluding A1C values obtained from administrative health data, 2) if findings differ when models include all participants regardless of A1C source, and a collection timing indicator variable (time since baseline, deviation from 18-month data collection timepoint), 3) the impact of using multiple imputation for missing data rather than full information maximum likelihood, 4) the impact of adjusting for changes in medication/insulin type between baseline and 6-months post-intervention follow-up, and 5) the impact of including the first measure of baseline A1C collected before the trial restart.

Elevated A1C We will assess group differences in elevated A1C as a binary outcome using mixed-effects logistic regression (odds ratios). Models will be adjusted for baseline A1C, and additional blocking variables (gender, recruitment location). To improve the precision of effect estimates, models will also be adjusted for age, race/ethnicity, educational attainment, number of children living in the home, and diabetes duration. Models will also include group (FoodRx vs comparison), and baseline A1C data source (study measured vs administrative health data) indicator variables. We will include random intercepts for participants (participant study ID) and primary care clinics (clinic study ID) to account for clustering of participants within clinics.

In addition to per-protocol and as-treated analyses, we will conduct sensitivity analyses for elevated A1C to examine 1) the impact of excluding A1C values obtained from administrative health data, 2) if findings differ when models include all participants regardless of A1C source, and a collection timing indicator variable (time since baseline, deviation from 18-month data collection timepoint), 3) the impact of using multiple imputation for missing data rather than full information maximum likelihood, 4) the impact of adjusting for changes in medication/insulin type between baseline and 6-months post-intervention follow-up, and 5) the impact of including the first measure of baseline A1C collected before the trial restart.

Fructosamine We will assess group differences in fructosamine as a continuous outcome using mixed-effects linear regression at 6- and 12-months. Models will be adjusted for baseline fructosamine, and blocking variables (baseline A1C, gender, recruitment location). To improve the precision of effect estimates, models will also be adjusted for age, race/ethnicity, educational attainment, number of children living in the home, and diabetes duration. Additionally, all models will include baseline A1C data source (study measured vs administrative health data), and group (FoodRx vs comparison). We will include random intercepts for participants (participant study ID) to account for within-subject correlation due to repeated measures, and for primary care clinics (clinic study ID) to account for clustering of participants within clinics.

In addition to per-protocol and as-treated analyses, we will conduct sensitivity analyses for fructosamine to examine 1) the impact of excluding A1C values obtained from administrative health data, 2) if findings differ when models include all participants regardless of A1C source, and a collection timing indicator variable (time since baseline, deviation from 18-month data collection timepoint), 3) the impact of using multiple imputation for missing data rather than full information maximum likelihood, 4) the impact of adjusting for changes in medication/insulin type between baseline and 6-months post-intervention follow-up, and 5) the impact of including the first measure of baseline A1C collected before the trial restart.

Clinical Health Markers, Secondary Outcomes

Systolic Blood Pressure We will assess group differences in systolic blood pressure as a continuous outcome using mixed-effects linear regression. Models will be adjusted for baseline systolic blood pressure, and blocking variables (baseline A1C, gender, recruitment location). To improve the precision of effect estimates, models will also be adjusted for age, race/ethnicity, educational attainment, number of children living in the home, and diabetes duration. Additionally, all models will include baseline A1C data source (study measured vs administrative health data), and group (FoodRx vs comparison) indicator variables. We will include random intercepts for participants (participant study ID) to account for within-subject correlation due to repeated measures, and for primary care clinics (clinic study ID) to account for clustering of participants within clinics.

In addition to per-protocol and as-treated analyses, we will conduct sensitivity analyses for systolic blood pressure to examine impact of excluding patients who were started on anti-hypertensive therapy.

Diastolic Blood Pressure We will assess group differences in diastolic blood pressure as a continuous outcome using mixed-effects linear regression. Models will be adjusted for baseline diastolic blood pressure, and blocking variables (baseline A1C, gender, recruitment location). To improve the precision of effect estimates, models will also be adjusted for age, race/ethnicity, educational attainment, number of children living in the home, and diabetes duration. Additionally, all models will include baseline A1C data source (study measured vs administrative health data), and group (FoodRx vs comparison) indicator variables. We will include random intercepts for participants (participant study ID) to account for within-subject correlation due to repeated measures, and for primary care clinics (clinic study ID) to account for clustering of participants within clinics.

In addition to per-protocol and as-treated analyses, we will conduct sensitivity analyses for diastolic blood pressure to examine impact of excluding patients who were started on anti-hypertensive therapy.

Lipids – Apolipoprotein B We will assess group differences in Apo B as a continuous outcome using mixed-effects linear regression. Models will be adjusted for baseline Apo B, and blocking variables (baseline A1C, gender, recruitment location). To improve the precision of effect estimates, models will also be adjusted for age, race/ethnicity, educational attainment, number of children living in the home, and diabetes duration. Additionally, all models will include baseline A1C data source (study measured vs administrative health data), and group (FoodRx vs comparison) indicator variables. We will include random intercepts for participants (participant study ID) to account for within-subject correlation due to repeated measures, and for primary care clinics (clinic study ID) to account for clustering of participants within clinics.

In addition to per-protocol and as-treated analyses, we will conduct sensitivity analyses for Apo B to examine the impact of excluding patients who were started on lipid-lowering therapy.

Lipids – Triglycerides We will assess group differences in triglycerides as a continuous outcome using mixed-effects linear regression. Models will be adjusted for baseline triglycerides, and blocking variables (baseline A1C, gender, recruitment location). To improve the precision of effect estimates, models will also be adjusted for age, race/ethnicity, educational attainment, number of children living in the home, and diabetes duration. Additionally, all models will include baseline A1C data source (study measured vs administrative health data), and group (FoodRx vs comparison) indicator variables. We will include random intercepts for participants

(participant study ID) to account for within-subject correlation due to repeated measures, and for primary care clinics (clinic study ID) to account for clustering of participants within clinics.

In addition to per-protocol and as-treated analyses, we will conduct sensitivity analyses for triglycerides to examine the impact of excluding patients who were started on lipid-lowering therapy.

Lipids – HDL We will assess group differences in HDL as a continuous outcome using mixed-effects linear regression. Models will be adjusted for baseline HDL, and blocking variables (baseline A1C, gender, recruitment location). To improve the precision of effect estimates, models will also be adjusted for age, race/ethnicity, educational attainment, number of children living in the home, and diabetes duration. Additionally, all models will include baseline A1C data source (study measured vs administrative health data), and group (FoodRx vs comparison) indicator variables. We will include random intercepts for participants (participant study ID) to account for within-subject correlation due to repeated measures, and for primary care clinics (clinic study ID) to account for clustering of participants within clinics.

In addition to per-protocol and as-treated analyses, we will conduct sensitivity analyses for HDL to examine the impact of excluding patients who were started on lipid-lowering therapy.

BMI We will assess group differences in BMI as a continuous outcome using mixed-effects linear regression. Models will be adjusted for baseline BMI, and blocking variables (baseline A1C, gender, recruitment location). To improve the precision of effect estimates, models will also be adjusted for age, race/ethnicity, educational attainment, number of children living in the home, and diabetes duration. Additionally, all models will include baseline A1C data source (study measured vs administrative health data), and group (FoodRx vs comparison) indicator variables. We will include random intercepts for participants (participant study ID) to account for within-subject correlation due to repeated measures, and for primary care clinics (clinic study ID) to account for clustering of participants within clinics.

In addition to per-protocol and as-treated analyses, we will conduct sensitivity analyses for BMI to examine the impact of BMI as an ordinal outcome (underweight/healthy weight, overweight, obese) using logistic regression models.

Waist Circumference We will assess group differences in waist circumference as a continuous outcome using mixed-effects linear regression. Models will be adjusted for baseline waist circumference, and blocking variables (baseline A1C, gender, recruitment location). To improve the precision of effect estimates, models will also be adjusted for age, race/ethnicity, educational attainment, number of children living in the home, and diabetes duration. Additionally, all models will include baseline A1C data source (study measured vs administrative health data), and group (FoodRx vs comparison) indicator variables. We will include random intercepts for participants (participant study ID) to account for within-subject correlation due to repeated measures, and for primary care clinics (clinic study ID) to account for clustering of participants within clinics.

In addition to per-protocol and as-treated analyses, we will conduct sensitivity analyses for waist circumference to examine the impact of waist circumference as a binary outcome for men (circumference ≥ 102 cm/40 inches), and women (circumference ≥ 88 cm/35 inches) using mixed-effects logistic regression models.

Need for Antihyperglycemic Medication/Insulin We will assess group differences in need for antihyperglycemic medication/insulin as an ordinal outcome using mixed-effects logistic regression. Models will be adjusted for baseline need for antihyperglycemic medication/insulin, and blocking variables (baseline A1C, gender, recruitment location). Additionally, all models will include baseline A1C data source (study measured vs administrative health data), and group (FoodRx vs comparison) indicator variables. To improve the precision of effect estimates, models will also be adjusted for age, race/ethnicity, educational attainment, number of children living in the home, and diabetes duration. We will include random intercepts for participants

(participant study ID) to account for within-subject correlation due to repeated measures, and for primary care clinics (clinic study ID) to account for clustering of participants within clinics.

In addition to per-protocol and as-treated analyses, we will conduct sensitivity analyses for need for antihyperglycemic medication/insulin to examine the impact of excluding patients whose medication/insulin therapy remained unchanged during the 3 months prior to their program start date, throughout the program, and when participants taking insulin are excluded.

Preliminary Auxiliary Variables

We will consider the following preliminary auxiliary variables based on theoretical relevance for the following outcomes.

Primary Outcome	
12-month A1C	Baseline A1C or fructosamine, systolic blood pressure, Apo B, BMI or waist circumference, duration of diabetes, insulin use, age, race/ethnicity, annual household income, educational attainment, number of children living in the home, diabetes duration;
Secondary Outcomes	
6-month A1C	Baseline A1C or fructosamine, systolic blood pressure, Apo B, BMI or waist circumference, duration of diabetes, insulin use, age, race/ethnicity, annual household income, educational attainment, number of children living in the home, diabetes duration;
18-month A1C	Baseline A1C or fructosamine, systolic blood pressure, Apo B, BMI or waist circumference, duration of diabetes, insulin use, age, race/ethnicity, annual household income, educational attainment, number of children living in the home, diabetes duration;
Elevated A1C	Baseline A1C or fructosamine, systolic blood pressure, Apo B, BMI or waist circumference, duration of diabetes, insulin use, age, race/ethnicity, annual household income, educational attainment, number of children living in the home, diabetes duration;
Fructosamine	Baseline A1C or fructosamine, systolic blood pressure, Apo B, BMI or waist circumference, duration of diabetes, insulin use, age, race/ethnicity, annual household income, educational attainment, number of children living in the home, diabetes duration;
Blood Pressure (systolic, diastolic)	Baseline A1C or fructosamine, BMI, employment status, age, race/ethnicity, annual household income, educational attainment, number of children living in the home, diabetes duration;
Lipids	Baseline A1C or fructosamine, BMI, employment status, age, race/ethnicity, annual household income, educational attainment, number of children living in the home, diabetes duration;
BMI	Baseline A1C, baseline waist circumference, blood lipids, employment status, physical activity level, age, race/ethnicity, annual household income, educational attainment, number of children living in the home, diabetes duration;
Waist Circumference	Baseline A1C, baseline BMI, blood lipids, employment status, physical activity level, age, race/ethnicity, annual household income, educational attainment, number of children living in the home, diabetes duration;
Need for medication/insulin	Fructosamine, baseline A1C, systolic blood pressure, blood lipids, insulin use, age, race/ethnicity, annual household income, educational attainment, number of children living in the home, diabetes duration;

